### 8.1. Discontinuation of Study Treatment

Participants may stop study medication on the basis of intolerance, as determined by AE, vital sign or physical examination findings, clinically important laboratory or ECG findings, or investigator opinion. If a participant does not tolerate study medication, the participant will be observed until the intolerable AE has either resolved or satisfactorily stabilized in the judgment of the investigator, and the participant will be withdrawn from the study.

AGN-242428

A participant will be permanently withdrawn from study medication if any of the criteria in **Table 8-1** are met and considered related to AGN-242428. Re-challenge with AGN-242428 will not be permitted.

**Table 8-1** Safety Criteria for Individual Participants Stopping Study Treatment

Parameter	Definition
Study treatment-related serious adverse event (SAE)	Study treatment-related SAE, as assessed by investigator
Increased liver transaminases a	Aspartate aminotransferase (AST) and/or alanine aminotransferase (ALT) increased to $\geq 5 \times$ upper limit of normal (ULN) c
Increased liver transaminases with increased total bilirubin (TBL) or increased INR	AST and/or ALT increased to $\geq 3 \times$ ULN AND TBL increased to $\geq 2 \times$ ULN or INR $> 1.5^c$
Increased liver transaminases with symptoms a,b	AST and/or ALT increased to $\geq 3 \times$ ULN with symptoms c
Decreased total leukocyte count a	Leukopenia to $< 3000/\mu\text{L}$ [ $< 3.0 \times 10^9/\text{L}$ ]
Decreased total neutrophil count a	Neutropenia to $< 1000/\mu\text{L}$ [ $< 1.0 \times 10^9/\text{L}$ ]
Decreased lymphocyte count a	Lymphopenia to $< 500/\mu\text{L}$ [ $< 0.5 \times 10^9/\text{L}$ ]
Decreased platelet count a	Thrombocytopenia to $< 100,000/\mu\text{L}$ [ $< 100 \times 10^9/\text{L}$ ]
Increased serum creatinine a	Serum creatinine increased to $\geq 2 \times$ ULN
Unspecified	Based on medical judgment of sponsor's Medical Safety Physician, Medical Expert and investigator

a To be confirmed by a repeat of the test within 2 to 5 calendar days.

b New or worsening symptoms believed to be related to liver injury (such as fatigue, nausea, vomiting, right upper quadrant pain or tenderness or jaundice) or hypersensitivity (such as fever, rash or eosinophilia  $> 5\%$ )

c Discontinuation of study treatment for abnormal liver function should be considered by the investigator when a participant meets one of the conditions outlined, or if the investigator believes that it is in best interest of the participant.

Liver Safety Suggested Actions and Follow-up Assessments Section can be found in Appendix 6, Section [12.6](#).

See the SoA (Section [2](#)) for data to be collected at the time of treatment discontinuation and follow-up and for any further evaluations that need to be completed.

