## 12.6. Appendix 6: Liver Safety: Suggested Actions and Follow-up Assessment

**Phase II** liver chemistry stopping criteria are designed to assure participant safety and to evaluate liver event etiology.

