### Phase II Liver Chemistry Stopping Criteria and Follow-Up Assessments

Liver Chemistry Stopping Criteria	
AST and/or ALT-absolute	AST and/or ALT $\geq 5 \times$ ULN
AST and/or ALT Increase	AST and/or ALT $\geq 3 \times$ ULN persists for $\geq 4$ weeks
Bilirubin or INR	AST and/or ALT $\geq 3 \times$ ULN and TBL $\geq 2 \times$ ULN or INR $> 1.5$
Cannot Monitor	AST and/or ALT $\geq 3 \times$ ULN and cannot be monitored weekly for 4 weeks
Symptomatica	AST and/or ALT $\geq 3 \times$ ULN associated with symptoms (new or worsening) believed to be related to liver injury or hypersensitivity
Potential Hy's Law cases	
AST, ALT, and Bilirubinb	AST and/or ALT $\geq 3 \times$ ULN and TBL $\geq 2 \times$ ULN and alkaline phosphatase $< 2 \times$ ULN

AGN-242428

Required Actions and Follow-up Assessments	
Actions	Follow-Up Assessments

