
 
• Immediately discontinue study treatment.
 
• Report the event to the sponsor within 24 hours.
 
• Complete the liver event eCRF, and complete a serious adverse event (SAE) data collection tool if the event also met the criteria for an SAE.b
 
• Perform liver chemistry follow-up assessments.
 
• Monitor the participant until liver chemistry test abnormalities resolve, stabilize, or return to baseline (see MONITORING).
 
• Do not restart/rechallenge participant with study treatment
 
• As restart/rechallenge is not allowed per protocol, permanently discontinue study treatment and continue participant in the study for any protocol specified follow-up assessments
 
	
 
• Viral hepatitis serology and other laboratory testing, as well as anti-nuclear antibody and anti-smooth muscle antibodyc
 
• Obtain INR and recheck with each liver chemistry assessment until the transaminases values show downward trend
 
• Obtain blood sample for pharmacokinetic (PK) analysis 48 hours after the most recent dosed
 
• Serum creatine phosphokinase (CPK) and lactate dehydrogenase (LDH)
 
• Fractionate bilirubin, if TBL <math>\geq 2 \times</math> ULN
 
• Obtain complete blood count with differential to assess eosinophilia
 
• Record the appearance or worsening of clinical symptoms of liver injury, or hypersensitivity, on the adverse event (AE) report form
 
• Record use of concomitant medications (including acetaminophen, herbal remedies, and other over-the-counter medications) on the concomitant medications eCRF.
 
• Record alcohol use on the liver event alcohol intake eCRF
 
 
If AST and/or ALT <math>\geq 3 \times</math> ULN AND bilirubin <math>\geq 2 \times</math> ULN:
 
 
• Repeat liver chemistry tests (include alanine transferase (ALT), aspartate transaminase [AST], alkaline phosphatase [ALP], total, direct, and indirect, bilirubin [TBL, DBL, IBL], gamma-glutamyl transferase [GGT], and lactate dehydrogenase [LDH]) and perform liver event follow-up assessments within 24 hours.
 
• Monitor participant twice weekly until liver chemistry test abnormalities resolve, stabilize, or return to baseline.
 
• A specialist or hepatology consultation is recommended.
 
 
If AST and/or ALT <math>\geq 3 \times</math> ULN AND bilirubin <math>< 2 \times</math> ULN:
 
 
• Type 1 anti-liver kidney microsomal antibodies, and quantitative total immunoglobulin G (IgG) or gamma
 

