	Study Stop Rules	A participant will be permanently withdrawn from study treatment if any of the criteria below are met and considered related to AGN-242428:

AGN-242428

Parameter Group	Parameter	Value
		
Study Treatment-related SAE
 
Decreased total leukocyte count; Leukopenia < 3000/<math>\mu</math>L (< 3.0 x 10^9/L)
 
Decreased total neutrophil count; Neutropenia < 1000/<math>\mu</math>L (< 1.0 x 10^9/L)
 
Decreased total lymphocyte count; Lymphopenia < 500/<math>\mu</math>L (< 0.5 x 10^9/L)
 
Decreased platelet count; Thrombocytopenia < 100,000/<math>\mu</math>L (< 100 x 10^9/L)
 
Increased serum creatinine; Serum creatinine > 2 x ULN
 
Unspecified safety concern; Upon request by investigator or Medical Safety Physician
 
Increased liver enzymes:
 
 
•ALT and/or AST <math>\geq</math> 5 x ULN
 
•ALT and/or AST <math>\geq</math> 3 x ULN AND TBL <math>\geq</math> 2 x ULN or INR > 1.5
 
•ALT and/or AST <math>\geq</math> 3 x ULN with symptoms
 

AGN-242428

**12.8. Appendix 8: Partial List of Prohibited Medications Which Are Sensitive Substrates for BCRP, OATP1B3, CYP2D6, and CYP2C8 and Strong Inhibitors or Inducers of CYP3A4**

This list of prohibited medications is provided as a guidance. Use of these medications is prohibited unless approved by the investigator or sponsor. This list is not comprehensive and the investigators will consult with the sponsor before allowing concomitant medication use during the trial.

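### Section 8.1, its footnote c and Appendix 6 conflict on whether a liver stop is mandatory, and Appendix 6 has two stopping criteria that Section 8.1 lacks

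*Protocol*

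**What the plan says.** Protocol Section 8.1 sets a firm rule, which begins "A participant will be permanently withdrawn from study medication if any of the criteria in" and points to its stopping table. A condition on cause is attached: the rule bites only where the listed criteria "are met and considered related to AGN-242428. Re-challenge with AGN-242428 will not be permitted". Appendix 7 repeats this in tabular form: "A participant will be permanently withdrawn from study treatment if any of the criteria below are met and considered related to AGN-242428". Both list three liver criteria: transaminases at or above 5 × ULN; at or above 3 × ULN with raised bilirubin or INR; and at or above 3 × ULN with symptoms.

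All three liver rows of Table 8-1 carry footnote c, which reads differently: "Discontinuation of study treatment for abnormal liver function should be considered by the investigator when a participant meets one of the conditions outlined". It goes on to allow a stop whenever the investigator thinks that best for the participant.

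Section 8.1 then refers the reader to Appendix 6, calling its content suggested actions. The appendix title agrees: "Appendix 6: Liver Safety: Suggested Actions and Follow-up Assessment". Its own table, however, is headed "Required Actions and Follow-up Assessments", and the first action is "Immediately discontinue study treatment". That action is permanent and has no relatedness condition. The appendix has five liver stopping criteria. The two additional ones are transaminases at or above 3 × ULN lasting at least 4 weeks, and the same level where follow-up is not feasible ("ULN and cannot be monitored weekly for 4 weeks").

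A further table in Appendix 6 allows continued dosing under closer monitoring for milder elevations. It sends anyone who later meets a stopping criterion back to Section 8.

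**The concern.** Liver injury is the safety risk that this protocol itself singles out. Section 5.5 reports transaminase elevations at one dose level in the earlier 4-week study, and this trial doses for 16 weeks. Section 5.4 relies on clearly defined handling of hepatic enzyme elevations as part of the design rationale.

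A stopping rule should give the same answer at each of about 40 centers. Here an investigator who follows Section 8.1 and footnote c may keep dosing a participant whom Appendix 6 would stop. The decision also matters because Section 7.2, Section 8.1 and Appendix 6 all bar rechallenge, so a stop cannot be reversed, while a wrong continuation leaves the participant exposed to the drug.

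**Working it through.** No published figure needs reproducing; the check is a comparison of rules.

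**Step 1: the texts side by side**

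| Source | Is stopping required? | Must it be judged related? | Liver criteria |
|---|---|---|---|
| Section 8.1 main text | Yes, permanent | Yes | 3 |
| Table 8-1 footnote c | To be considered | Not mentioned | the same 3 |
| Appendix 7 | Yes, permanent | Yes | 3 |
| Appendix 6 stopping table | Yes, immediate and permanent | No | 5 |

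The Appendix 6 count leaves out its separate row for potential Hy's Law cases. The difference is 5 − 3 = 2 criteria.

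**Step 2: two test cases**

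- *Case A.* Confirmed ALT at or above 5 × ULN, judged unrelated. The Section 8.1 mandate does not apply, and footnote c leaves the decision to the investigator. Appendix 6 requires an immediate stop.
- *Case B.* ALT between 3 and 5 × ULN for at least 4 weeks, no symptoms, normal bilirubin and INR. Appendix 6 requires a stop. Its monitoring table then refers the reader to Section 8, where no liver row of Table 8-1 fits. Only the general medical-judgment row remains.

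Case A survives the most generous reading of footnote c, namely that it covers only events judged unrelated. Case A is exactly such an event.

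**Step 3: all rule combinations**

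Take participants with AST or ALT at or above 3 × ULN and seven two-way features: level (3 to <5, or ≥5 × ULN), bilirubin ≥2 × ULN, INR >1.5, symptoms, judged related, lasting ≥4 weeks, and weekly monitoring possible. That gives 2^7 = 128 profiles. These are combinations of conditions, not patient frequencies.

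- A Table 8-1 liver criterion is met in (16 − 1) × 8 = 120 profiles. Half are judged related, so the Section 8.1 text mandates a stop in 60.
- Appendix 6 mandates a stop in all but the 2 profiles with no stopping feature: 128 − 2 = 126.
- Gap: 126 − 60 = 66. Of these, 60 arise because the event is judged unrelated. The other 6 meet only the two criteria missing from Table 8-1 (3 combinations of duration and monitoring × 2 for relatedness).
- If footnote c overrides the main text, the 60 mandates through the liver rows also become matters for consideration. A potential Hy's Law case judged related would still be caught by the treatment-related SAE row, because Section 9.2.8 makes such a case an SAE.

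**Step 4: two smaller mismatches**

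- The continue criterion in Appendix 6 names ALT only and omits INR. ALT 3.5 × ULN with INR 1.6, bilirubin below 2 × ULN and no symptoms fits both the stop and the continue criteria. So does ALT 4 × ULN with AST 6 × ULN and normal INR.
- Section 8 takes anyone who stops study drug out of the study. Appendix 6 keeps a participant stopped for a liver criterion in the study for follow-up.

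**The case against.** The best defence is that the texts can be read together. Section 8.1, Section 9.2.8 and the appendix title all call the Appendix 6 actions suggested. Section 9.4.4 refers to Section 8 and Appendix 6 as guidance on liver monitoring. The monitoring table routes stopping cases to Section 8. The two lists can be taken as cumulative, and Section 8.1 never tells a site to continue, so a site that always stops breaches nothing. The 66 profiles therefore mostly show one text requiring what another leaves open.

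Much of that is fair, but it does not settle the matter. The appendix heads its own actions as required. The routing to Section 8 leads back to the shorter list, the relatedness condition and footnote c. Neither place says that the lists are cumulative.

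Three stronger readings are tempting and are not supported:

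- *The same participant is told both to stop and to continue.* The overlap in the continue criterion is a drafting fault. A later line in the same table says that meeting a stopping criterion at any time ends the continue path.
- *The immediate stop contradicts the repeat test at 2 to 5 days in footnote a.* Appendix 6 asks for a repeat at 24 to 72 hours when bilirubin is below 2 × ULN. With a day taken as 24 hours, one draw at 48 to 72 hours meets both. Whether dosing is held meanwhile cannot be judged, because the schedule of activities and part of Section 5.1 are not visible.
- *Divergent stops remove Week 16 PASI values, given the observed-data analysis in SAP Section 10.0.* That relies on the Section 8 withdrawal rule and overlooks the Appendix 6 instruction to keep these participants in the study. The visit windows are not visible either.

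The safeguards are real: sponsor discussion of immediate safety concerns (Section 9), sponsor notice within 24 hours (Appendix 6), the Hy's Law laboratory alert (Section 9.2.8) and the scheduled DMC reviews (Section 5.1). They make divergence between sites less likely, but none says which rule applies.

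**Conclusion.** The point holds and should be fixed. The liver stopping rules conflict on two matters: whether a stop is mandatory, including whether relatedness matters, and which criteria trigger it. The clearest case is a confirmed transaminase value of at least 5 × ULN judged unrelated. The second is a case that meets only one of the two criteria found in Appendix 6 alone.

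The size can be stated only in terms of rules: three criteria against five, and a stop required by Appendix 6 but not by the Section 8.1 text in 66 of 128 combinations. The visible text gives no event rate, so no count of affected participants is offered and no effect on the primary endpoint is claimed. The conclusion rests on visible wording alone. Hidden parts of the schedule of activities might add retest instructions.

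**What to change.** Amend the protocol as follows.

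1. State in Section 8.1 that Appendix 6 controls for liver events.
2. List its five criteria in Table 8-1 and Appendix 7.
3. Exempt the liver rows from the condition that the event be considered related.
4. Replace footnote c with: *Study treatment must be discontinued when any liver criterion is met; the investigator may also stop in the participant's best interest.*
5. Retitle Appendix 6 as required actions, and match the reference to it in Section 8.1.
6. Change the continue criterion in Appendix 6 to AST and/or ALT ≥3 × ULN with both <5 × ULN, bilirubin <2 × ULN and INR ≤1.5. Keep the existing conditions on symptoms and weekly monitoring.
7. State in Section 8 that participants stopped for liver criteria remain in the study for the Appendix 6 follow-up.

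Making Appendix 6 the controlling text is a choice; it is the more protective one for a known risk. Holding the dose until a retest is not recommended, because it would loosen Appendix 6 and would have to be reconciled with its bar on restarting.

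The cost is amendment wording and a memo to sites, with no added participants or staff. The downside is that a few more participants may stop, because a judgment of unrelatedness no longer exempts them.

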### 8.1.1. Temporary Discontinuation

The DMC allows for temporary discontinuation of dosing pending further analysis of possible safety issues (an option open to the DMC).

### 8.1.2. Criteria for Study Termination

The study may be terminated for any of the following reasons:

- Sponsor decides to terminate the trial for any reason.

AGN-242428

- There are multiple similar AEs or SAEs that are deemed by the sponsor and its medical experts as a safety signal that poses a medically unacceptable risk to patients.

## 8.2. Withdrawal from the Study

A participant may withdraw from the study at any time at his/her own request, or may be withdrawn at any time at the discretion of the investigator for safety, behavioral, compliance, or administrative reasons. If the participant withdraws consent for disclosure of future information, the sponsor may retain and continue to use any data collected before such a withdrawal of consent. If a participant withdraws from the study, he/she may request destruction of any samples taken and not tested, and the investigator must document this in the site study records.

See the schedule of activities (Section 2) for data to be collected at the time of study discontinuation and follow-up and for any further evaluations that need to be completed.

Participants withdrawn due to AEs will not be replaced. Participants who are withdrawn for other reasons may be replaced at the discretion of the sponsor if deemed necessary to ensure sufficient data are obtained at each dose level to adequately assess safety.

## 8.3. Lost to Follow-Up

A participant will be considered lost to follow-up if he or she repeatedly fails to return for scheduled visits and is unable to be contacted by the study site.

The following actions must be taken if a participant fails to return to the clinic for a required study visit:

The site must attempt to contact the participant and reschedule the missed visit as soon as possible and counsel the participant on the importance of maintaining the assigned visit schedule and ascertain whether or not the participant wishes to and/or should continue in the study.

Before a participant is deemed lost to follow-up, the investigator or designee must make every effort to regain contact with the participant (where possible, 3 telephone calls and, if necessary, a certified letter to the participant's last known mailing address or local equivalent methods).

These contact attempts should be documented in the participant's medical record.

Should the participant continue to be unreachable, he/she will be considered to have withdrawn from the study with a primary reason of lost to follow-up.

AGN-242428

## 9. Study Assessments and Procedures

Study procedures and their timing are summarized in the schedule of activities (Section 2).

Protocol waivers or exemptions are not allowed.

Immediate safety concerns should be discussed with the sponsor immediately upon occurrence or awareness to determine if the participant should continue or discontinue study treatment.

Adherence to the study design requirements, including those specified in the schedule of activities, is essential and required for study conduct.

To be eligible to take part in the study, all screening evaluations must be completed and reviewed to confirm that potential participants meet all eligibility criteria. The investigator will maintain a screening log to record details of all participants screened and to confirm eligibility or record reasons for screening failure, as applicable.

The maximum amount of blood collected from each participant over the duration of the study, including any extra assessments that may be required, will not exceed 440 mL. Repeat or unscheduled samples may be taken for safety reasons or for technical issues with the samples.

### 9.1. Efficacy Assessments

Efficacy assessments and data will be collected for all participants receiving AGN-242428 or placebo. Efficacy will be assessed by medical review of PASI, total BSA and PGA scores and changes from baseline values. PD measures including IL-17A and IL-17F plasma concentrations will be determined, but the assessment of efficacy will be determined primarily by clinical signs and symptoms and improvement in clinical psoriasis scores.

#### 9.1.1. Determination of Percent Body Surface Area

The % body surface area (BSA) will be determined using the participant's palm area to approximate 1% of BSA (handprint method). To the extent possible, the same trained and qualified dermatologist will complete estimation of % BSA for a participant at all study timepoints when % BSA is assessed including screening and baseline. The same trained and qualified dermatologist must determine the baseline and Week 16 % BSA.

The palmar surface of the participant's hand (entire palmar surface including fingers) will approximate 1% of BSA:

- Head and neck = 10% (10 palms)
- Upper extremities = 20% (20 palms)
- Trunk (axillae and groin) = 30% (30 palms)
- Lower extremities (buttocks) = 40% (40 palms)

Protocol 1957-201-001 Amd 2

## AGN-242428

Estimate the total BSA affected and record in the eCRF. If multiple small lesions are present, combine several to equal 1 participant palm. If there is central clearing, include only the edge and not the areas that have cleared.

### 9.1.2. Psoriasis Area and Severity Index

The PASI score will be determined by the same trained and qualified dermatologist, to the extent possible, at all study timepoints when PASI score is assessed including the screening and baseline visits. Assessment of PASI at Day 1 (baseline) and Week 16 will be completed by the same trained and qualified dermatologist.

The PASI score combines the severity (erythema, induration, and desquamation) and percentage of affected area. Each of 4 body regions will be assessed for surface area involvement and graded for erythema, thickness (induration) and scaling (desquamation). By combining the individual scores from each body region, the total PASI score is determined.

### 9.1.2.1. Surface Area Involvement by Body Regions

The 4 body regions to be assessed are:

- Head and neck – 10% of total BSA
- Upper extremities – 20% of total BSA
- Trunk including axillae and groin – 30% of total BSA
- Lower extremities including buttocks – 40% of total BSA

The surface area covered by plaques in each body region is determined using the palm method (handprint method) and assigned a score for that body region according to the scoring criteria tabulated below. Surface area involvement of each of the 4 anatomic regions is scored on a scale of 0 (no involvement of that specific body region) to 6 (90% to 100% involvement of that specific body region).

